1.2. Investigators

The CM is responsible for maintaining an updated list of all Principal Investigators (PI's), investigation sites and institutions.

PRINCIPAL INVESTIGATOR

Visits will be conducted at subject's own home or at a clinic or at Coloplast A/S, if subjects prefer not to have visits at own home.

CONFIDENTIAL

Page 9 of 34

2. Introduction

The prevalence of urinary incontinence in adult men has been estimated to range between 11-34% in older men, and 3-5% in younger and middle-age men [1]. The products available for men with mild-to-moderate incontinent are typically adult pads or diapers, e.g. Tena for men. Pads and diapers are not always optimal, as they are seen as large/bulky to use and store, and there is a risk of leakage, if the pad/diaper displaces during use, and urinary leaks are not absorbed by the product.

Coloplast has developed a new product for men with mild-to-moderate urinary incontinence, which is placed directly on the penis, and where the absorber (pad) are placed in a water-tight pocket. The product is the size of the smallest incontinence pads on the market for men, and can fit into to pockets of most trousers.

3. Objective(s) and hypotheses of the clinical investigation

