4.2.4. Demography and potential compromising factors

Assessments:

- Age
- Level of incontinence (how often, how much)
- Usual product/management routine (using a product, what type, how many)
- Reason for incontinence (if known)
- Duration of incontinence (for how long has subject had the current issues)

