5.6. Comparator product(s)

There is no comparator product in this investigation.

6. Subjects

Twenty male subjects who are suffering from mild-to-moderate urinary incontinence, will be enrolled in this study.

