6.1. Inclusion and exclusion criteria

To be included in the investigation, the subjects must comply with the selection criteria described below

Inclusion criteria:	Justification:

1. Have given written informed consent2. Male3. Be at least 18 years of age and have full legal capacity4. Suffering from urinary incontinence equivalent to using up to 6 pads or 2 diapers per day5. Have had current incontinence issues for at least 3 months6. Able to understand patient information and able to change the product himself7. Up to 6 of the subjects can be users who are using an intermittent catheter due to retention, but who are also dribble incontinent in-between catheterizations, and hence need a product to handle the incontinence.8. Able to fit the test product.	
1. To meet the Helsinki Declaration2. To meet the target population of this device3. To meet the Helsinki Declaration4. To meet the target population of this device5. To be sure subjects meets target population of this device6. To meet the Helsinki Declaration7. To meet the target population of this device8. To meet the target population of this device

CONFIDENTIAL

Page 13 of 34

Exclusion criteria:	Justification:

 1. If experiencing incontinence less than once per week 2. Bedridden, using wheelchair or using a walking aids regularly 	
 1. To meet the target population of this device 2. To meet the target population of this device

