Frequency of success in support of "stays in place"	Did the product stay in place during use?	Subject	X	Not at all – no – Don't know – yes – yes very much
Frequency of answers pertaining to yes in support of "future use"	If, possible, would you want to use the product in the future?	Subject	X	Yes - No
Frequency of answers pertaining to yes in support of "reliability for in-home use"	Do you rely on the product being functional for use at home?	Subject	X	Yes - No
Frequency of answers pertaining to yes in support of "reliability for use away from home"	Do you rely on the product being functional for using away from home? By this we mean e.g. at work, during sports, being social or when traveling.	Subject	X	Yes - No
Frequency of answers pertaining to yes in support of "future recommendation"	Would you recommend the product to others?	Subject	X	Yes - No
Frequency of answers pertaining to yes in support of "preference"	Do you prefer this product over your normal product / normal management routine?	Subject	X	Yes - No

CONFIDENTIAL

Page 21 of 34

Additional assessments				
What size product did you use	Subject	X		Large – Regular - both
If both – which size did you prefer	Subject	X		Large - Regular
How many products did you typically use per day? (categories)	Subject	X	• 1 • 2 to 3 • 4 to 5 • 6 or more	
In average, for how long did you typically use one product? (categories)	Subject	X	• 1-2 hours • 3-4 hours • 5-6 hours • 7-12 hours • More than 12 hours	
Where did you use the products? (categories, more answers are allowed)	Subject	X	• At home • At work • At social event(s) • While doing sports • During travel/trip • At night	
Did you experience leakage? (Y/N)	Subject	X	Yes - No	
If yes – when? (categories, more answers are allowed)	Subject	X	• While sitting • While standing • While moving about • While laying down Other, please describe _____	

CONFIDENTIAL

Page 22 of 34

If yes – how often? (categories, more answers are allowed)	Subject	X	• Several times a day • Once a day • 5-6 times during the week • 2-4 times during the week • 1 during the week

CONFIDENTIAL

Page 23 of 34

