9.1. Statistical design, method and analytical procedures

Endpoints and assessments

All baseline assessments, endpoints and other measurements will be reported by descriptive statistics and/or listed.

Analysis populations

Intention to Treat (ITT), Safety and Per Protocol (PP) populations will be defined at a formal data review meeting just before database lock. As a minimum, the clinical manager and the statistician will be involved in the classification of subjects.

The Safety population (basis for the AE summary) will constitute subjects with valid informed consent.

The ITT population (Full analysis set) will constitute all subjects, with valid informed consent, who have been exposed to at least one product and furthermore, with information recorded on at least one endpoint (non-missing).

No formal PP population is planned. However, if additional explorative analyses are deemed necessary, a PP population will be established, based on a subset of the ITT population.

Individual endpoints/data points may be excluded from analysis, even though the corresponding subject belongs to the ITT population. This situation could arise due to protocol violations, where, at one visit, the primary endpoint could be affected, but same effect did not occur at the following visit.

All analysis will be based upon the ITT population and AEs will be summarized based on the safety population.

Any exclusion of subjects or data points from any of the populations must be documented.

Descriptive statistics for continuous variables are presented with N, Mean, SD (standard deviation), Median, Min and Max), where N denotes the number of subjects contributing with non-missing data. For discrete variables, descriptive statistics are presented with N and percentage, where percentage is based on the total number of subjects/observations with non-missing data.

A significance level of alpha equal to 0.05 (two-sided) is applied.

All endpoints will be analyzed by an exact test in the binomial distribution (proportion is equal to 50%), where the frequency of success or will estimated with 95% confidence limits.

The two highest or best categories in questions obtained from a 5-point ordinal scale is defined as a success. Likewise, the answer yes, is defined a success, obtained from questions with a yes/no categorical option.

In favor of a claim, the lower 95% confidence limit must be above 50%.

Other summaries and analyses can be made, if relevant.

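### The preference item does not say that it means leakage management, so up to 6 of 20 men could answer it with their catheter in mind

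*Combined protocol and SAP*

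**What the plan says.** - **The item.** Table 2 in section 7.3 asks "Do you prefer this product over your normal product / normal management routine", with Yes and No as the only answers. No explanation is attached, whereas the item on reliability away from home, in the same table, does explain what is meant.
- **The reference.** Section 5.6 states "There is no comparator product in this investigation". The comparison is therefore with whatever each man takes his normal product or routine to be.
- **The men.** Section 6 plans for 20. Inclusion criterion 7 in section 6.1 says "Up to 6 of the subjects can be users who are using an intermittent catheter due to retention", provided that they are also "dribble incontinent in-between catheterizations, and hence need a product to handle the incontinence". Section 6.2 names the sponsor's database of intermittent-catheter users as one of three recruitment routes. Its search criteria include catheter use but not use of an absorbent product.
- **The analysis.** For Yes/No items section 9.1 states "Likewise, the answer yes, is defined a success". All analyses use the ITT population. A claim is supported when the lower 95% limit exceeds 50% (sections 9.1 and 9.4).
- **What is recorded at baseline.** Section 4.2.4 lists the usual product or management routine among the Part 1 items. Section 9.1 does not link it to the preference item.

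**The concern.** A man who catheterises for retention and also dribbles has two routines: the catheter, and whatever he uses for leakage. The device collects leaked urine and does not empty the bladder. Asked about his normal management routine, he could answer No because the device does not replace his catheter, or Yes because it beats his pad. Both are reasonable readings of the same words, and both go into one proportion.

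This is the only endpoint in Table 2 that sets the product against anything else, and the secondary objective is to support commercial claims. If some men answer about the catheter, a failed claim may only show that a leakage product is no substitute for catheterisation. A reader of the report could not tell which comparison the percentage describes.

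**Working it through.** The plan gives no sample-size calculation or power for this endpoint, so there is no figure to reproduce. The check is what the pass rule tolerates.

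**Inputs.** n = 20 (section 6); at most 6 catheter users, so at least 14 others (section 6.1); exact binomial method, two-sided alpha 0.05, reference 50%, lower 95% limit above 50% (sections 9.1 and 9.4); percentages on non-missing answers (section 9.1); drop-outs not replaced (section 9.2). The number of catheter users who would answer about the catheter is not given; the range is 0 to 6.

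**Formula.** For x Yes answers out of n, the exact (Clopper-Pearson) lower limit is the 0.025 quantile of Beta(x, n − x + 1).

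**Step 1: threshold at n = 20.**
- 15/20: Beta(15, 6) gives 50.9%, a pass (two-sided p = 0.041).
- 14/20: Beta(14, 7) gives 45.7%, a fail (p = 0.115).

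At most 5 Noes are tolerated. The method for the interval does not change this: 14/20 also fails with Wilson (48.1%), mid-p (47.7%) and Wald (49.9%) limits.

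**Step 2: catheter-framed Noes, with every other man answering Yes.**

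| Answers | Such Noes | Yes | Lower limit | Result |
|---|---|---|---|---|
| 20 | 5 | 15/20 | 50.9% | pass |
| 20 | 6 | 14/20 | 45.7% | fail |
| 19 | 5 | 14/19 | 48.8% | fail |
| 18 | 5 | 13/18 | 46.5% | fail |
| 17 | 5 | 12/17 | 44.0% | fail |

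For contrast, 14 Yes out of 14 non-catheter men taken alone gives 0.025^(1/14) = 76.8%.

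**Step 3: between the extremes (assumed rates, all six places filled, 20 answers).** If the other 14 all say Yes, the claim passes when at least one catheter user says Yes. With q the Yes probability of each catheter user, the pass probability is 1 − (1 − q)^6:
- q = 0: 0%
- q = 0.10: 1 − 0.90^6 = 47%
- q = 0.25: 1 − 0.75^6 = 82%
- q = 0.50: 1 − 0.50^6 = 98%

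If the other 14 say Yes with probability 0.90 instead, the same four values of q give 0%, 15%, 40% and 75%, against 99% when the catheter users share the 0.90 rate. These rates are illustrations; the documents give none.

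**The case against.** The best defence is context. The item names the normal product first. Criterion 7 admits catheter users because they need a product for leakage, and criterion 4 defines incontinence in pads or diapers. Another Part 2 question asks about managing the man's incontinence. Subjects are trained on the device, and the investigator or delegate oversees completion at V2. A man might well see that the cover has nothing to do with his catheter. This stands in part: the catheter reading is plausible but not documented. It would go too far to infer that catheter users will read the item that way, or that a few Noes from them defeat the claim. With 20 answers, all six places must be filled and all six men must answer No before the claim fails despite unanimous support elsewhere.

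A man's own usual management is also a coherent reference in a single-arm study. The Introduction says "The products available for men with mild-to-moderate incontinent are typically adult pads or diapers", but it does not confine the preference claim to those products. A reader might infer that men with no usual product make the result invalid and should be left out. The documents do not support that: preferring the cover to going without is a meaningful answer. Leaving men out would also depart from the ITT rule and raise the required share from 15/20 (75%) to 15/19 (79%), or to 12/14 (86%) if only 14 remained.

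The stakes are limited. This is one of 21 secondary claims in an exploratory study without formal hypotheses, and the catheter reading would withhold a claim rather than create one.

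What does not stand is that the plan already handles the matter. Section 9.1 allows other summaries if relevant, but that is optional and could be chosen after the results are seen. The Part 1 record can show who answered differently. It cannot show what each man was comparing with.

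**Conclusion.** The point holds in limited form. The wording leaves the reference open for a subgroup that the plan admits on purpose, and the forced Yes/No answer gives no way to tell the readings apart afterwards.

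The size is uncertain: between 0 and 6 of 20 answers could be affected. In the extreme case of six such Noes among 20 answers, or five among 17 to 19, the claim fails even if all other men prefer the product. Five among 20 answers still pass. The failing cases assume that five or six catheter users answer and that all of them answer No. When support among the other men is high but not unanimous, fewer such Noes matter, as the illustration at a 0.90 rate shows.

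The primary comfort endpoint and the other secondary claims are not touched.

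**What to change.** 1. Reword the item in Table 2: *Do you prefer this product over the product or routine you normally use to manage urine leakage (not your catheter)?*
2. Keep the ITT denominator and the existing pass rule for this claim.
3. Pre-specify in section 9.1 a descriptive breakdown of this item by the usual product or routine recorded in Part 1 (pad or diaper, other, none) and by catheter use (yes or no). Check that Part 1 separates the catheter from the leakage product, since its listing does not name the catheter.
4. If the answers are already collected, which is possible given the section 6.5 dates, specify the breakdown before database lock. It will show whether catheter users answered differently, but it will not resolve what they compared with.

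**Cost.** One reworded question, one sentence in section 9.1 and one extra table, with no new data beyond Part 1. If the rewording counts as a change of assessment method, section 11 requires an entry in the change log and notification to or approval by the ethics committee. The breakdown will rest on small groups and should be reported without tests.

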Clinical Investigation Plan

CP326

Exploratory study of a new urine collection device for men

June 2020 – December 2020

1st of December 2020

NCT04672993|

This confidential document is the property of Coloplast A/S.
No unpublished information contained herein may be
disclosed without written approval of Coloplast A/S.

CONFIDENTIAL

Page 1 of 34

CHANGE LOG

VER-SION NUM-BER	ISSUED BY (INITIALS)	COMMENTS (MAJOR CHANGES SINCE LAST REVISION)
1.0	[name]	First approved version
2.0	[name]	
Updated due to comments from Ethics Committee and minor internal changes
 
Section 1.1 – Sponsor representatives: Contact information for Data manager and Clinical Manager have been updated.
 
Section 6.2 – Recruitment and enrolment: Only potential subjects in the Coloplast Database, that have consented to be contacted regarding clinical investigations, will receive an invitation letter.
 
Section 7.3 – Flow-charts: Some answers have been updated to be clearer.

CONFIDENTIAL

Page 2 of 34

SYNOPSIS OF THE CLINICAL INVESTIGATION

The aim of the study is to evaluate the subjects experience of the test product "Contend Protective Cover" - a urine collection device for males.

Objective

Primary objective:

- To investigate the comfort of using the test product.

Secondary objective:

- To evaluate handling and subject experience during wear in support of commercial claims.

Design of the investigation

An open-labelled, single arm study design was chosen for study CP326.

A single arm study over a duration of 1 week + up to 3 days extra

V0: Inclusion

V1: Test visit 1

V2: Test visit 2 and termination

Subjects may be interviewed up to two times either in-person or over the phone and these interviews will preferably be conducted at V2. Second interview can be conducted up to 6 months after V2.

Primary endpoint and secondary endpoint(s)

Primary endpoint:

- Frequency of success in support of "comfortable"

Secondary endpoints:

- Frequency of success in support of various commercial claims

Please see [Table 2](#) for a detailed listing of all endpoints

Population/subjects

Twenty male subjects who are suffering from mild-to-moderate urinary incontinence, will be enrolled in this study.

To be included in the investigation, the subjects must comply with the selection criteria described below

Inclusion criteria:	Exclusion criteria
1. Have given written informed consent 2. Male	1. If experiencing incontinence less than once per week

CONFIDENTIAL

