4.1. General

An open-labelled, single arm study design was chosen for study CP326 with a duration of 1 week + up to 3 days extra as illustrated below.

V0: Inclusion, V1: Test visit 1,

V2: Test visit 2 and termination

Subjects may be interviewed up to two times either in-person or over the phone and these interviews will preferably be conducted at V2. Second interview can be conducted up to 6 months after V2.

CONFIDENTIAL

Page 10 of 34

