4.3. Discussion of clinical investigation design

An open-labelled, single arm study design was chosen for this study with a duration of a test period of 1 week. The study cannot be blinded because only one test product is tested. The study period of one week is assessed as adequate for evaluation of the endpoints.

5. Investigational device and comparator(s)

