7.1.1. Visits

Visit 0 (Inclusion visit)

If a potential subject is interested in participating after the first contact, a visit (visit 0) will be arranged at subject's home or at a clinic or at Coloplast, if subjects prefer not to have visits in own home, in a room reserved to ensure privacy and quiet surroundings. When arranging the visit, it will be ensured, that the subject has received the Subject Information Form prior to the visit. The subjects will receive both written and verbal information to ensure that the subject understands what was read and explained and can freely agree to participate in the investigation. The subject will, beforehand, also be informed about the possibility of bringing a companion to Visit 0 and to any possible subsequent visits. During the visit the principal Investigator, or delegate, will provide oral information about the investigation based on the Subject Information Form. The subject has the right to wait before deciding on participation.

If/when subjects decide to participate, they will be asked to sign the Informed Consent Signature Form. If a subject so desires, and it is certain that it is understood what the investigation entails, and the relevant form has been signed, the subjects are considered enrolled in the investigation. Enrolled subjects that are deemed eligible per the inclusion/exclusion criteria are allocated a subject number. Visit 0 and visit 1 can be combined.

Visits 1 (V1)

During visit 1, part 1 of the questionnaire Table 1 (demographic questions) will be completed by the Principal Investigator, or delegate. The subject will be trained in the use of the test product per IFU. The subjects are instructed to continue their everyday life and change test product whenever they feel the need to.

Visits 2 (V2)

During visit 2, the Principal Investigator, or delegate will ensure part 2 of the questionnaire [Table 2](#) will be completed by subjects. Potential (S)AE's will be captured by the Principal Investigator, or delegate. Hereafter termination If appropriate, subjects may be interviewed regarding use of the test product by a Coloplast representative at V2, otherwise an alternative time for interview may be scheduled.

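### The leakage-frequency item has no recall window and counts leaks per week in a study that may run to 10 days, so the same leakage rate may be coded differently.

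*Combined protocol and SAP*

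**What the plan says.** Leakage is listed in Table 2 (section 7.3) under the additional assessments and is answered by the subject at V2. A yes/no question comes first, then one on circumstances, then the frequency item: "If yes – how often? (categories, more answers are allowed"). Neither the yes/no question nor the frequency item states a recall period. The frequency item has five options. Two are daily rates (several times a day, once a day). Three are counts within the week: "5-6 times during the week", a 2-4 option and a single-leak option.

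On duration, the synopsis has "A single arm study over a duration of 1 week + up to 3 days extra" and section 4.1 says the same. Section 4.3 describes the design "with a duration of a test period of 1 week" and adds: "The study period of one week is assessed as adequate for evaluation of the endpoints". On the start of the period, section 7.1.1 says: "Visit 0 and visit 1 can be combined". No section says whether the extra days are days of product use before V2 or slack elsewhere in the schedule.

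**The concern.** A weekly count is well defined only if the respondent knows which week is meant. Here the period before V2 may exceed a week and the item does not say what to do about that. One man may total all leaks since V1, another may think of a typical week, and a third may recall the last seven days. Two men with the same leakage rate could then fall in different rows of the table.

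The ambiguity is fixed when the man answers, so it cannot be repaired in analysis. Section 8 relies on edit checks to ensure that every field is completed, so a man whose total fits no option may be pushed into a neighbouring one without trace. With at most 20 men, each misplaced answer moves a category by at least 1/20 = 5 percentage points. Containing urine is the purpose given for the device in section 5.2, and the leakage questions are the ones that ask directly about its failure.

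**Working it through.** The plan states no figure on this point, so there is none to reproduce.

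**Inputs from the plan.** Period length d = 7 to 10 days (synopsis, section 4.1), or 7 days (section 4.3). Option values as listed in Table 2.

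**Assumptions.** The extra days are days of use. The man counts over the whole period. On a strict reading, once a day means exactly d leaks and several times a day means at least 2d. Leakage rates are not in the documents, so a range is shown.

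**Step 1: excess time, d/7 − 1.** 8 days: 14.3%. 9 days: 28.6%. 10 days: 42.9%.

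**Step 2: totals that match no option.**

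| Days | Below once a day | Above once a day (strict reading) |
|---|---|---|
| 7 | none | 8-13 |
| 8 | 7 | 9-15 |
| 9 | 7-8 | 10-17 |
| 10 | 7-9 | 11-19 |

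The lower gap opens only when the period exceeds a week. The upper gap is already there at exactly 7 days.

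**Step 3: category shift at a constant rate.** Multiply the 7-day total by 10/7. Four leaks become 5.7, which moves from the 2-4 option towards the 5-6 option. Five become 7.1 and six become 8.6, both in the lower gap.

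**Step 4: illustrative probabilities.** Take a Poisson count with mean m = (leaks per 7 days) × 10/7, and P(7-9) = Σ e^(−m) m^k / k! for k = 7, 8, 9.

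| Assumed leaks per 7 days | m over 10 days | P(5-6) over 7 days | P(5-6) over 10 days | P(7-9) over 10 days |
|---|---|---|---|---|
| 1 | 1.43 | 0.004 | 0.015 | 0.001 |
| 2 | 2.86 | 0.048 | 0.135 | 0.026 |
| 3 | 4.29 | 0.151 | 0.284 | 0.130 |
| 4 | 5.71 | 0.260 | 0.327 | 0.282 |
| 5 | 7.14 | 0.322 | 0.268 | 0.387 |
| 6 | 8.57 | 0.321 | 0.177 | 0.395 |

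The lower gap matters from about 3 leaks per week upwards and is negligible at 1 or 2.

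**Step 5: the same totals read as a weekly rate.** Multiply the 10-day total by 7/10. Totals of 7, 8 and 9 become 4.9, 5.6 and 6.3 per week, all nearest to the 5-6 option. The lower gap therefore exists only for a man who counts the whole period.

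**The case against.** A reader might infer that men seen later do report over up to 43% more time. The documents do not establish this. Section 4.3 gives a one-week test period, the extra days are not placed in the schedule, and V0 and V1 may be separate visits. The options refer to the week and two of the five are daily rates, so many men would answer with a frequency, and Step 5 shows that such answers find an option. This stands, and it limits the point to an undefined window. It does not remove the point: when V0 and V1 are combined, as section 7.1.1 permits, V1 to V2 is the only between-visit interval left for extra days.

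A reader might also infer that the extra days are what leaves totals without an option. That is true only of the lower gap.

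Nor is leakage frequency the only evidence on containment. The dry feeling, confident management, urine smell and reliability items also bear on it and are endpoints under the success rule, and product faults that cause leakage are reportable device deficiencies (section 16.3).

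The item feeds no claim, pass criterion or comparison, and longer counting would make the device look worse, not better. That also stands. Finally, Table 2 shows English wording for a study recruiting in Denmark, so whether the version the men saw named a window cannot be checked.

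**Conclusion.** The point holds as a minor questionnaire fault. The item sets no recall window, and its weekly options do not match a study that may last up to 10 days. If the extra days are days of use, the counting period may differ by up to 43% between men, and a whole-period count over 10 days has a probability of about 0.13 to 0.40 of falling in the uncovered 7-9 range at assumed rates of 3 to 6 leaks per week. These figures rest on a full 10 days of use, whole-period counting and Poisson leakage. The share of men using the extra days is not given, so the effect on the final table cannot be estimated.

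Two further faults need none of these assumptions about the extra days. Multiple answers make the frequency categories non-exclusive, and on a strict reading totals of 8-13 have no option even at 7 days.

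Only a descriptive additional assessment is affected. The primary comfort endpoint and the rule that the lower 95% confidence limit exceed 50% (sections 9.1 and 9.4) do not depend on it.

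**What to change.** Reword the item as: *In the last 7 days of use, how often did you experience leakage?* Allow one answer only. Use contiguous options, for example 1 time, 2-4 times, 5-6 times, about once a day, more than once a day. Because the preceding yes/no question has no window, add an option for no leakage in the last 7 days; otherwise a man who leaked only earlier would have nothing to tick. A fixed window alone would close the 7-9 gap but leave the upper gap and the multiple answers in place, so all three changes are needed.

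Tabulate the V1 to V2 interval beside the item. Reconcile sections 4.1 and 4.3 on the length of use, and say where the extra days fall.

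The change adds no visits and no new data collection. It is not quite free: section 11 names assessment methods among significant changes, so it would need agreement between the sponsor and the principal investigator, an entry in the change log, and notification to or approval by the ethics committee before use.
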